4. To compare proportion of patients needing extra prednisone to control flares.
5. To compare the proportion of patients with intra-articular injections.
6. To compare the proportion of patients who have at least one flare confirmed by the investigator during the protocol.
7. To compare the area under the curve of the means of the FLARE at one year with a self-assessment questionnaire.
8. To compare the proportion of patients in DAS28 remission and in DAS28 low disease activity at 7 and 12 months between the groups.
9. To compare the medians of HAQ at 4, 7 months and 1 year between the groups.
10. To compare the medians of RAID at 4, 7 months and 1 year between the groups.
11. To compare the medians of the EQ-5D at 4, 7 months and 1 year between groups.
12. To compare the medians of the FACIT-F at 4, 7 months and 1 year between groups.
13. To compare the proportion of patients with “serious” adverse events at 1 year between the groups.

STAR – Statistical Analysis Plan
V3, June 2023

Page 9 of 96

5) Study Population

a. Inclusion Criteria

- Patients aged ≥ 18 years.
- Fulfilling the 2010 ACR/EULAR criteria for RA.
- Treated with a stable dose of sDMARDs or bDMARDs for at least 3 months.
- Who have been treated with prednisone or prednisolone for at least 6 months.
- With a stable dose of prednisone or prednisolone of 5mg/day for at least 3 months.
- With a DAS28 ≤ 3.2 for at least 3 months.
- Patients with health insurance.
- Patients who have signed a written informed consent form.

b. Non-inclusion Criteria

- Any chronic condition that would need long term corticoid use (e.g. chronic lung diseases).
- Evidence of a flare within the last 3 months.
- Evidence of an allergy or intolerance to hydrocortisone or prednisone.
- Chronic idiopathic, or autoimmune clinical adrenal insufficiency.
- GC joint injections within the last 3 months or scheduled in the next 3 months.
- Any GC intake expected more than $>5\text{mg/day}$ within the next 12 months (i.e. administration with rituximab, multiple sclerosis requiring frequent GC infusions,...).
- Any disease with GC contraindication.
- Association with sultopride and with live vaccines.
- Significant trauma or major surgery within the 3 months prior to the baseline visit.
- Scheduled surgery in the next 12 months.
- Fibromyalgia.
- Foreseeable poor compliance with the strategy.

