You felt a greater need for help for several days in a row due to your polyarthritis

Synacthen test at M4, M7, M9, M12, VAdd 1, VAdd 2

- Test carried out (yes/no) [CRF p60, p85, p102, p127, p144, p155]
 - If Yes, specify:
 - Cortisol without stimulation (yes/no) [CRF p60, p85, p102, p127, p144, p155]
 - Test value (µg/100mL) [CRF p60, p85, p102, p127, p144, p155]
 - Cortisol 60 minutes after stimulation with 0.25 mg of Synacthène® (yes/no) [CRF p60, p85, p102, p127, p144, p155]
 - Test value (µg/100mL) [CRF p60, p85, p102, p127, p144, p155]
 - Is the Synacthen test considered pathological? (yes /no) [Derived variable]
 - If No, if cortisol at 60 minutes is normal and the patient is on open-label hydrocortisone, specify:
 - Maintenance of hydrocortisone, specify dosage (mg/day) (yes/no) [CRF p61, p86, p103, p128, p145, p156]
 - If Yes, specify why
 - Hydrocortisone withdrawal (yes/no) [CRF p61, p86, p103, p128, p145, p156]
 - Other, specify (yes/no) [CRF p61, p86, p103, p128, p145, p156]
 - Accuracy (listing) [CRF p61, p86, p103, p128, p145, p156]
 - If Yes, is the patient summoned again for the introduction of hydrocortisone in accordance with the protocol? (yes /no) [CRF p61, p86, p103, p128, p145, p156]
 -]If No, another attitude is adopted towards the results of a pathological Synacthen test, please specify:
 - The patient was already on Hydrocortisone before this visit (yes/no) [CRF p61, p86, p103, p128, p145, p156]
 - Other, specify (yes/no) [CRF p61, p86, p103, p128, p145, p156]
 - Accuracy (listing) [CRF p61, p86, p103, p128, p145, p156]

STAR – Statistical Analysis Plan
V3, June 2023

Page 54 of 96

We will identify discordant patients, that is to say, those having a pathological test after recalculation [derived variable] although they were declared as normal in the eCRF, as well as patients who did not receive a open-label hydrocortisone until the next visit as planned in the protocol (patients to be classified in the protocol deviation group).

STAR – Statistical Analysis Plan
V3, June 2023

Page 55 of 96

End of study sheet

- Follow-up duration variable] [Derived
- Did the patient complete the trial according to protocol? (yes /no) [CRF p157]
 - Specify the reason for premature termination:
 - Adverse event or serious adverse event (yes/no) [CRF p157]
 - Resumption of RA activity/prescription of long-term prednisone or prednisolone (yes/no) [CRF p157]
 - Patient's refusal to prosecute (yes/no) [CRF p157]

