In the randomized population, those lost to follow-up, that is to say patients for whom the endpoint is missing, will be analyzed as a failure of the strategy (conservative approach). This result will be easy to collect, blindly.

For explanatory variables, descriptive analyzes will be conducted on available data. The number of non-missing subjects (n) will be specified for each explanatory variable.

STAR – Statistical Analysis Plan
V3, June 2023

Page 62 of 96

3) Primary analysis of the primary endpoint (ITT)

The main endpoint will be compared in the two groups using a Chi2 test after verification of the application conditions: theoretical numbers greater than 5. In the event that the application conditions are not respected, a Fisher's exact test will be used.

The significance threshold for the tests is set at 0.05.

STAR – Statistical Analysis Plan
V3, June 2023

Page 63 of 96

4) analysis of the primary endpoint (ITT)

Sensitivity analyses of the primary outcome will include:

- An analysis on complete data (excluding subjects lost to follow-up and with missing data on the primary endpoint) (analysis 1)
- A stratified descriptive analysis (without testing) according to the duration of corticosteroid therapy before inclusion (≤ 2 years or > 2 years) (analysis 2)
- An analysis adjusted for potentially confounding criteria, based on a multiple logistic regression model adjusted for the randomization group as well as the initial characteristics if there is a significant imbalance between the comparison groups regarding the following characteristics (analysis 3):
 - Duration of corticosteroid therapy ≤ 2 years / > 2 years [CRF p19]
 - Duration of remission (in years) [Derived variable]
 - Duration of corticosteroid therapy at 5 mg/day
 - Duration of treatment with prednisone at 5 mg/day (in months) [Derived variable]
 - Age at inclusion date [Derived variable]
 - Sex [CRF p9]
 - Duration of illness on inclusion (in years) [Derived variable]
 - Rheumatoid factors (positive/negative) [Derived variable]
 - Anti-CCP2 (positive/negative) [Derived variable]
 - Presence of erosions [CRF p9]
 - Charlson Index [Derived variable]
 - HAQ score [Derived variable]
 - Synthetic background treatment during the study [Derived variable]
 - Biological background treatment during the study [Derived variable]
 - DAS28 at inclusion [Derived variable]
 - VAS fatigue at inclusion [CRF p16]

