- In the event of missing data at one or more visits, we will impute the non-missing values of the randomization group from which the patient came at the visit in question by the median value.

Patient FLARE scores should have a large number of missing data (questionnaires poorly completed during follow-up). These scores present will be described in each group using the mean, standard deviation, median and interquartile range. In the event of missing data on one of the items, the value of the missing item will be replaced by the median value of the item at the visit concerned according to the patient's randomization group.

No bivariate analysis will be performed on these scores.

STAR – Statistical Analysis Plan
V3, June 2023

Page 79 of 96

8) Proportion of patients in remission or at low activity level according to the DAS28 at 7 and 12 months

Proportion of patients in remission and with low disease activity at 7 months and one year. Patients with a DAS28 < 2.6 will be considered in remission, patients with a DAS28 between 2.6 and 3.2 will be considered in LDA.

The DAS28 formula is as follows:

$$\text{DAS28} = (0.56 * \text{sqr}(\text{TJC})) + (0.28 * \text{sqr}(\text{SJC})) + (0.7 * \text{ln}(\text{VS})) + (0.014 * \text{GH})$$

Where **TJC** = Number of painful joints [CRFp72, p114]
SJC = Number of swollen joints [CRFp72, p114]
VS = the sedimentation rate [CRFp84, p126]
GH = overall health represents the patient's assessment of disease activity on a scale of 0 to 100 where 100 corresponds to maximum activity [CRFp81, p123].
 The DAS28 is calculated automatically in the e-CRF.

Variable name	Derivations
Remission according to DAS28 (Yes No)	
From the DAS28 scores at M7 and M12 (variable present in the database or programmed), we define two modalities:
 
 • " If yes : 
 ○ DAS28 < 2.6 • " Not if : 
 ○ DAS28 ≥ 2.6 
For each of times M7 and M12, a variable will be created using the same methods.

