Low level of activity according to DAS28 (yes/no)	
From the DAS28 scores at M7 and M12 (variable present in the database or programmed), we define two modalities:
 
 • " If yes : 
 ○ DAS28 ≥ 2.6 and < 3.2 • " Not if : 
 ○ DAS28 ≥ 3.2 ○ OR if DAS28 > 2.6 
For each of times M7 and M12, a variable will be created using the same methods.

Remission or low level of activity according to DAS28 (Yes No)	
From the variables " Remission according to DAS28 " and " Low activity level according to DAS28 " [Derived variable], we define two modalities:
 
" If yes :
 
 • " Remission according to DAS28 " = Yes OR • " Low activity level according to DAS28 " = Yes 
" Not if :
 
 • " Remission according to DAS28 " = No AND • " Low level of activity according to DAS28 " = No 
For each of times M7 and M12, a variable will be created using the same methods.

STAR – Statistical Analysis Plan
V3, June 2023

Page 80 of 96

The proportion of patients in remission or at a low level of activity will be compared in the two groups using a Chi² test after verification of the application conditions: theoretical numbers greater than 5. In the event that the application conditions are not not respected, a Fisher exact test will be used.

The significance threshold for the tests is set at 0.05.

STAR – Statistical Analysis Plan
V3, June 2023

Page 81 of 96

9) HAQ-DI score at 4, 7 and 12 months

Functional impairment assessed by the Health Assessment Questionnaire (HAQ) at baseline, 4, 7 months and one year.

The HAQ will be calculated at baseline [CRFp25-26], at 4 [CRFp49-50], 7 months [CRFp74-76] and one year [CRFp116-117], and is expressed as continuous data.

The HAQ-DI SCORE at inclusion 4, 7 and 12 months will be compared in the two groups using a Student t test if the application conditions are met and a non-parametric Mann-Whitney Wilcoxon test otherwise.

The significance threshold for the tests is set at 0.05.

STAR – Statistical Analysis Plan
V3, June 2023

Page 82 of 96

10) RAID score at 4, 7 and 12 months

Patient-reported outcomes assessed by the Rheumatoid Arthritis Impact of Disease (RAID) questionnaire at baseline, 4, 7 months, and 1 year.

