Depending on the numbers, the proportion of patients having had one or more serious adverse events can be compared between the two groups using a Chi2 test after checking the conditions of application: theoretical numbers greater than 5. In the case where the conditions applications would not be respected, a Fisher exact test will be used.

The significance threshold for the tests is set at 0.05.

STAR – Statistical Analysis Plan
V3, June 2023

Page 86 of 96

SECURITY ANALYSIS

The population for the safety analysis is composed of all included and randomized patients who received at least one dose of treatment (prednisone and hydrocortisone placebo / Hydrocortisone and prednisone placebo).

Patients will be analyzed in the weaning strategy group actually received (particularly in the event of an error in allocation of treatment and placebo).

All expected or unexpected serious adverse events, and all unexpected non-serious adverse events, occurring from the date of signing the consent, during the duration of the study and until the end of the participant's follow-up provided for by the research (1 year); or up to 24 hours after stopping the experimental treatment (prednisone or hydroxycortisone) in the event of premature exit from the study, will be collected and will be included in an adverse event form after coding according to the dictionary. standardized medical MedDRA.

Adverse events will be described according to the different hierarchical levels of the MedDRA classification. The listing of these adverse events will be presented after grouping into "Preferred Term" and organization by "System-Organ Class". The listing will contain the following information:

- identifier of the subject and center,
- date and time of start of the adverse event,
- date and time of end of the adverse event (or mention of the persistence of the adverse event),
- description of the event ("Reported Term" and "Preferred Term"),
- gravity ,
- attributability to the test or the treatment of the test,
- action on the processing of the test,
- other action and evolution.

Will be presented by arm (prednisone and hydrocortisone placebo / Hydrocortisone and prednisone placebo):

- The incidence of adverse events according to their causality and severity.
- The incidence of adverse events leading to treatment discontinuation.
- Adverse events occurring between signing the consent and the first use of the experimental technique.

STAR – Statistical Analysis Plan
V3, June 2023

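### Endpoint 8 (DAS28 remission or low activity at M7 and M12) has no denominator and no rule for a missing DAS28, so early leavers not seen at the visit fall out of the test and can bias it in either direction

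*SAP*

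**What the plan says.** Secondary objective 8 in the SAP is "To compare the proportion of patients in DAS28 remission and in DAS28 low disease activity at 7 and 12 months between the groups". In the analysis section for endpoint 8, the derivations start "From the DAS28 scores at M7 and M12 (variable present in the database or programmed), we define two modalities". Remission is Yes below 2.6 and No at or above 2.6. Low activity is Yes from 2.6 to below 3.2, and No at or above 3.2 or above 2.6. The combined variable is Yes if either of these is Yes. The only test stated is: "The proportion of patients in remission or at a low level of activity will be compared in the two groups using a Chi² test", with Fisher's exact test as fallback. The section names no analysis population, denominator or missing category.

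The missing-data section under the primary endpoint says that "those lost to follow-up, that is to say patients for whom the endpoint is missing, will be analyzed as a failure of the strategy". For other variables it says only: "For explanatory variables, descriptive analyzes will be conducted on available data". The end-of-study sheet lists, among the reasons for premature termination, "Resumption of RA activity/prescription of long-term prednisone or prednisolone (yes/no". The sample size section anticipates 20% loss to follow-up among 102 randomised patients, 51 per arm.

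**The concern.** A patient with no DAS28 at the visit satisfies neither the Yes nor the No definition, so the test runs on the patients who were measured. One route to being unmeasured is leaving the study because the disease became active, which is close to the outcome itself. The denominator then depends on the outcome. Each arm's observed rate rises when its leavers do worse than its average patient, and the amount depends on how many leave. Both strategies withdraw glucocorticoid, so unequal disease-driven exits are plausible. The comparison could show a difference in disease control that does not exist, or shrink or enlarge one that does.

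No other sentence in the SAP fills the gap. Where the authors wanted a rule for a secondary endpoint, they wrote one: rescue glucocorticoid (endpoint 4) and flare (endpoint 6) count missing as No, and the FLARE score (endpoint 7) imputes the arm median. Endpoint 8 has none.

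**Working it through.** **The plan's own figure.** The SAP gives no figure for endpoint 8. Its sample size for the primary endpoint reproduces. With 30% vs 60%, two-sided 5% and 80% power, n = [1.96·√(2·0.45·0.55) + 0.842·√(0.3·0.7 + 0.6·0.4)]² / 0.30² = 42 per arm, and 42 × 1.2 = 50.4, rounded up to 51. So 51 per arm and about 20% loss are the plan's own scale. True remission/low-activity rates, the exit split by arm and the leavers' status are assumptions below.

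**Formula.** Let p be the true rate among all randomised patients in an arm, L the fraction without a DAS28, and s the share of those who are not in remission or low activity. The observed-case rate is (p − L(1 − s)) / (1 − L). It exceeds p by L/(1 − L) × [p − (1 − s)]: an arm is inflated when its leavers respond less often than its average patient.

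**A true difference of 20 points (50% vs 70%), exits averaging 20%.** Power is for a two-proportion test on 51 × (1 − L) patients per arm; with all 51 per arm it is 54%.

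| Exits, arm 1 vs arm 2 | s | Observed rates | Difference | Power |
|---|---|---|---|---|
| 30% vs 10% | 100% | 71.4% vs 77.8% | 6.3 points | 10% |
| 30% vs 10% | 75% | 60.7% vs 75.0% | 14.3 points | 28% |
| 30% vs 10% | 50% | 50.0% vs 72.2% | 22.2 points | 54% |
| 25% vs 15% | 100% | 66.7% vs 82.4% | 15.7 points | 37% |
| 25% vs 15% | 75% | 58.3% vs 77.9% | 19.6 points | 48% |
| 20% vs 20% | 100% | 62.5% vs 87.5% | 25.0 points | 75% |

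First row: 0.50/0.70 = 0.714 and 0.70/0.90 = 0.778. Last row: 0.50/0.80 = 0.625 and 0.70/0.80 = 0.875. With equal exits the true gap is divided by 0.80, which makes 20 points into 25.

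**No true difference (31 of 51 in each arm, 60.8%), all leavers non-responders.**

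| Leavers | Observed | False difference | Chi² p |
|---|---|---|---|
| 10 vs 10 | 31/41 vs 31/41 (75.6% each) | 0 | 1.00 |
| 5 vs 10 | 31/46 vs 31/41 (67.4% vs 75.6%) | 8.2 points | 0.40 |
| 6 vs 14 | 31/45 vs 31/37 (68.9% vs 83.8%) | 14.9 points | 0.12 |
| 5 vs 15 | 31/46 vs 31/36 (67.4% vs 86.1%) | 18.7 points | 0.050 |

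The false difference favours the arm that lost more. With 51 as denominator in each arm it is zero in every row.

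**Simulated false-positive rate** (40,000 trials per scenario, equal true rates, all leavers non-responders). On observed cases, at a 60% true rate it is 13.7% with 10% vs 20% leaving and 51.8% with 10% vs 30%. At a 50% true rate the figures are 10.3% and 31.0%. Counting missing as not in remission or low activity gives 5.4% to 6.0% in the same scenarios.

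**Two further points in the same section.** Remission is derived at each visit, but the stated test covers only the combined category, so the remission comparison named in objective 8 has no test. In the low-activity derivation, a DAS28 strictly between 2.6 and 3.2 meets both the Yes condition and the No condition (above 2.6), and a value below 2.6 meets neither.

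**The case against.** A reader might infer that every patient whose RA becomes active, or who restarts glucocorticoid, is lost to endpoint 8. The SAP does not support that. Added long-term corticosteroid for a flare is recorded at M4, M7, M9, M12 and the additional visits, and the primary endpoint and endpoint 1 both read corticosteroid use at M12. Such patients can stay in the study, attend and be scored. Resumption of activity is one of several termination reasons, with no frequency given. Any DAS28 assessment after exit may be set out in the protocol, which is not at hand. The limit "or up to 24 hours after stopping the experimental treatment (prednisone or hydroxycortisone) in the event of premature exit from the study" concerns adverse events, not DAS28. Exclusion from the test is a consequence of the definitions; the SAP does not state it in words.

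A reader might also infer that the bias always hides a true difference, or take the 6-point row as its expected size. Neither follows. The 20% is loss for any reason; splitting it 30% vs 10% and making every leaver a non-responder are assumptions. With half the leavers not in low activity, the same split gives 22 points, and equal exits give 25. Leavers who restarted prednisone may be back in low activity by M12, so counting them as non-responders defines a composite outcome and does not recover a known value.

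These objections limit the certainty, size and direction of the error. They do not supply the missing rule.

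**Conclusion.** The concern holds as a gap in the analysis rule: endpoint 8 is scored on observed DAS28 values only, with no denominator and no handling of missing values, although one listed exit reason is tied to the outcome. If leavers are mostly not in remission or low activity, observed rates are inflated, and sufficiently unequal exits bias the comparison towards the arm that loses more. Under assumed true rates of 50% vs 70%, the observed difference runs from about 6 to 25 points across the splits shown. Under equal true rates, 5 vs 15 leavers produce about 19 points from nothing. Size and sign rest on an exit split and on a leaver status that the SAP does not give. This is one of 13 secondary endpoints; the primary analysis is unaffected. The untested remission comparison and the faulty low-activity condition are smaller, separate defects in the same section.

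**What to change.** In the endpoint 8 section, for M7 and M12:

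- Use all randomised patients as the denominator.
- Count a missing DAS28 after premature termination as not in remission and not in remission or low activity, in line with the primary endpoint's convention.
- State how a missing DAS28 is handled in patients who continue (missed visit, or a missing joint count, sedimentation rate or patient assessment).
- Add an observed-case sensitivity analysis, and report the number missing and the reasons by arm.
- Compare remission (DAS28 below 2.6) on its own at each visit, as well as the combined category.
- Rewrite the low-activity No condition so that it covers values below 2.6 and no longer overlaps the Yes range.

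The cost is SAP wording. Reported rates will be lower, and the composite will count as non-responders some patients who left for unrelated reasons or who were back in low activity; the sensitivity analysis shows how much this matters.
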